All data outlined in Table 1 will be collected for all participants up until and including the time of withdrawal from the study. Recruitment will occur for this study on an ongoing basis until 200 participants are recruited and have completed the study. Participants withdrawn from the study will follow the outlined “Transition to Standard Care” and “Medication Discontinuation Process” outlined below.

Participant Compensation

Compensation for In-Person Participants

Participants will receive \$125 CAD at week 2 visits, \$125 at week 4 visits and \$250 at week 8 visit. Participants may also choose to receive the full \$500 at the end of the study (week 8).

Participants who complete the EEfRT task will be awarded their earnings from this task in addition to the \$500. The EEfRT may also be administered as a stand alone assessment (i.e., outside of fMRI) or as part of the fMRI assessment. Participants who complete the EEfRT will be compensated with what they earn from this task in addition to the \$500. Participants that complete exploratory blood work will also be compensated \$50.

Compensation for Remote Participants

Participants will receive \$31.25 CAD at week 2 visits, \$31.25 at week 4 visits and \$62.50 CAD at week 8 visit. Participants may also choose to receive the full \$250 at the end of the study (week 8).

Study Medication: Vortioxetine

AGE: 18-64

Participants receiving vortioxetine will be provided 10 mg/day on days 1–14 of the treatment period, and will be titrated to 20 mg/day at the start of week 3 (day 15) based on study clinician judgment. For the remaining 6 weeks, the dose of vortioxetine will be 20 mg/day, unless adjudicated otherwise by a study clinician.

AGE: >65

Per product monograph, participants 65+ receiving vortioxetine will be provided 5 mg/day on days 1–14 of the treatment period, and will be titrated to 10 mg/day at the start of week 3 (day 15) based on study clinician judgment. For the remaining 6 weeks, the dose of vortioxetine will be 10 mg/day, unless adjudicated otherwise by a study clinician.

Age: 65

Individuals aged 65 may start at 5mg or 10mg on days 1-14, and this dose may be titrated to 10mg or 20mg, respectively, at the start of week 3 based on the recommendation of the study physician.

Vortioxetine will be encapsulated in a capsule shell made of Capsugel® empty hard gelatin capsule (non-porcine / pure-bovine origin). Colorant: Swedish Orange OpC307. Size: AA.

Excipients: Gelatin, Red Iron Oxide, Titanium Dioxide. The filler used for both the active capsule with vortioxetine and the entire placebo capsule is Capsulac® 60 Lactose Monohydrate (Ph.Eur/USP-NF/JP).

Individuals aged 65 may start at 5mg or 10mg on days 1-14, and this dose may be titrated to 10mg or 20mg, respectively, at the start of week 3 based on the recommendation of the study physician.

Side effects

- Serotonin Syndrome has been reported with serotonergic antidepressants (SSRIs, SNRIs, and others), including with vortioxetine both when taken alone, but especially when coadministered with other serotonergic agents (including triptans, tricyclic antidepressants, fentanyl, lithium, tramadol, tryptophan, buspirone, and St. John's Wort).
- Treatment with serotonergic antidepressants (SSRIs, SNRIs, and others) may increase the risk of abnormal bleeding. Patients should be cautioned about the increased risk of bleeding when Vortioxetine is coadministered with nonsteroidal anti-inflammatory drugs (NSAIDs), aspirin, or other drugs that affect coagulation.
- Activation of Mania/Hypomania can occur with antidepressant treatment.
- Angle Closure Glaucoma: Angle closure glaucoma has occurred in patients with untreated anatomically narrow angles treated with antidepressants.
- Hyponatremia can occur in association with the syndrome of inappropriate antidiuretic hormone secretion (SIADH).

Most Common

- Gastrointestinal adverse events; including nausea, vomiting, constipation/diarrhea. Highest incidence occurs during the first week of treatment: 21-32%
- Sexual dysfunction: 14-34%

Less Common: 1-10%

- Dry mouth
- Dyspepsia (discomfort of the abdomen)
- Dizziness
- Somnolence/sedation
- Fatigue
- Insomnia
- Abnormal dreams
- Hyperhidrosis (increase sweating)
- Arthralgia (joint pain)
- Decreased appetite
- Itchy skin
- Nasopharyngitis

Rare: Less than 1%

- Nervous system disorders
- Skin and subcutaneous tissue disorders
- Psychiatric disorders
- Abnormal bleeding

- Clinical worsening or suicide risk

Post-Market Adverse Reactions

The following adverse events have been identified during post-approval use of Vortioxetine. These events are reported voluntarily from a population of uncertain size, and it is not possible to reliably estimate their frequency or establish a causal relationship to drug exposure.

- Hyperprolactinaemia
- Acute pancreatitis
- Anaphylactic reaction
- Serotonin syndrome, headache
- Agitation, aggression
- Angioedema
- Hemorrhage (including contusion, ecchymosis, epistaxis, gastrointestinal or vaginal hemorrhage)

Please see product monograph for full details.

Contraindications

Hypersensitivity to vortioxetine or any components of the formulation. Angioedema has been reported in patients treated with vortioxetine. The use of monoamine oxidase inhibitors (MAOI) intended to treat psychiatric disorders with vortioxetine or within 21 days of stopping treatment with vortioxetine is contraindicated because of an increased risk of serotonin syndrome. The use of vortioxetine within 14 days of stopping an MAOI intended to treat psychiatric disorders is also contraindicated.

Starting vortioxetine in a patient who is being treated with MAOIs or antibiotics such as linezolid or intravenous methylene blue is also contraindicated because of an increased risk of serotonin syndrome.

Storage

Medication will be stored at room temperature in a locked cabinet and office space at BCDF ([name]).

Transition to Standard of Care

Patients will be informed of the transition to standard of care procedures (outlined here) post study prior to providing consent to participate in the study. These procedures will also be outlined in writing in the patient consent form itself.

Upon completing the 8-week course of vortioxetine, if patients benefit from this drug, they will be encouraged to continue the treatment with their most responsible physician (MRP). Patients will be notified prior to study consent that not all drug plans will cover the cost of vortioxetine. Should patients wish to continue to use this drug post-study when they do not have coverage, they will be personally responsible for the costs.

If patients do experience side effects during the study, the study physician will make a recommendation regarding the discontinuation or dose reduction of the medication for the

remainder of the study. If participants do not experience any improvement upon study completion in mood or cognition, the medication will be gradually discontinued over a two-week period upon study completion (end of week 8). Participants will take half of their final dose of vortioxetine during the first week post-study and no medication during the second week of discontinuation. Participants will be provided with one week worth of medication for this discontinuation process but will not be provided any further supply thereafter.

Vortioxetine discontinuation process

At the end of week 8, patients will be seen by the study physician and provided with half of current vortioxetine dosage for a period of 1 week. This is in keeping with the product insert, although vortioxetine does not cause discontinuation syndrome. During the second week, patients will not be on medication and will be seen by the study physician at the end of two weeks, to ensure that there are no risks or adverse events during this time period. This visit with the clinician is post-study, and not part of the study visits. Patients are encouraged to contact the study team in the event that they would like to be scheduled with the physician earlier.

Data Handling

Personal Data Protection

All data collection material will be de-identified. Participant records will be distinguished using participant identification (PID) numbers.

Data Collection and Retention

The majority of data will be collected electronically through the secure RedCap platform. Participants will also sign the consent form via the RedCap platform after a thorough discussion with research staff during the in-person screening visit. Participants will receive an electronic copy of their consent form via email. Participants may also receive a printed copy of the consent form if this is preferred. Records and documents pertaining to the conduct of the study as well as all data collected as part of the study will be retained in a secure place for 25 years in accordance with Health Canada regulations. All data collected throughout the study will be kept with membership of the BCDF for 25 years. Data collected as hard copies (e.g. paper format) may be digitized and stored electronically, after which the hard copies will be destroyed (even before the 25 years).

Participants' de-identified plasma samples (labelled with participant ID) will be stored in a -80 degrees Celsius freezer for a maximum of 15 years from the time of collection. Participants may choose to withdraw their samples at any time.

Participant Protection

Participants will not be placed at any risk as a result of the study. Information obtained will be maintained in a secure and confidential fashion. No participant will be coerced and/or placed under duress to complete study procedures.

Adverse Events

An adverse event (AE) is the development of an undesirable medical condition or the deterioration of a pre-existing medical condition following or during exposure to a

pharmaceutical product, whether or not considered causally related to the product. An undesirable medical condition can be symptoms (e.g., nausea, chest pain), signs (e.g., tachycardia, enlarged liver) or the abnormal results of an investigation (e.g., laboratory findings, electrocardiogram). In clinical studies, an AE can include an undesirable medical condition occurring at any time, including run-in or washout periods, even if no study treatment has been administered.

Pregnancy in itself is not regarded as an AE unless there is a suspicion that an investigational product may have interfered with the effectiveness of a contraceptive medication. Follow-up of adverse events should be based upon the clinical judgement of the investigator.

Assessment of Intensity

Each AE will be classified according to the following criteria:

- Mild: The AE does not interfere in a significant manner with the participant's normal level of functioning.
- Moderate: The AE produces some impairment of functioning, but is not hazardous to the participant's health.
- Severe: The AE produces significant impairment of functioning or incapacitation and is a definite hazard to the participant's health.

When changes in the intensity of an AE occur more frequently than once a day, the maximum intensity for the experience should be noted. If the intensity category changes over several days, those changes should be recorded separately (with distinct onset dates).

Severity versus Seriousness

It is important to distinguish between serious and severe AEs. Severity is used to describe the intensity of a specific event while the event itself, however, may be of relatively minor medical significance (such as severe headache). This is not the same as "seriousness," which is based on participant/event outcome at the time of the event. An AE of severe intensity need not necessarily be considered serious. For example, nausea that persists for several hours may be considered severe nausea, but not an SAE. On the other hand, a stroke that results in only a limited degree of disability may be considered a mild stroke but would be an SAE. Symptoms associated with overdose should be reported as AEs. For further information regarding overdose, see section.

Recordings of Adverse Events

Adverse events will be collected from baseline to endpoint. At each visit, subjects will be asked if they have experienced any health problems or side effects since the previous visit. All AEs will be recorded appropriately, whether or not considered related to the investigational product. This will include AEs spontaneously reported by the patient and/or observed by members of the research team as well as AEs reported in response to a direct question (e.g., "Have you experienced any health problems or side-effects since your last visit?").

For each AE, the following parameters will be described:

- Discovery (i.e., spontaneous or solicited)

- Start date
- Stop date or ongoing
- Action taken with regards to investigational product
- Outcome if the AE caused the patient to discontinue the investigational product
- A statement if the AE fulfills the criteria for a SAE or not
- The investigator's assessment of the causal relationship between the event and the investigational product
- Intensity of the AE
 - Mild (awareness of sign or symptom, but easily tolerated)
 - Moderate (discomfort sufficient to cause interference with normal activities)
 - Severe (incapacitating, with inability to perform normal activities)
- Resolution

Assessment of Causality

Each AE will be assessed as to its relationship to the IP, based on the following criteria. Although the attribution by the investigator will be collected for reported events, for analytic purposes a temporal association with the use of the IP will be assumed sufficient for at least plausible association.

- Not related: No causal relationship exists between the IP and the AE, but an obvious alternative cause exists, eg, the participant's underlying medical condition or concomitant therapy.
- Possibly related: A connection with the administration of the IP appears unlikely, but cannot be ruled out with certainty. An AE may be considered possibly related if or when it meets 2 of the following criteria: (1) it follows a reasonable temporal sequence from administration of the IP; (2) it could not readily have been produced by the participant's clinical state, environmental or toxic factors, or other modes of therapy administered to the participant; or (3) it follows a known pattern of response to the IP.
- Related: There is a reasonable/plausible possibility that the AE may have been caused by the IP.

When assessing the relationship to the IP, the following criteria will be considered:

- Known class effect
- Biological plausibility
- Lack of alternative explanation—concomitant drug or disease

Action Taken Regarding Investigational Product

Dose modifications of IP (ie, dose not changed, drug withdrawn, drug interrupted, or dose increased).

- Not Applicable: Participant died, study treatment had been completed prior to reaction/event, or reaction/event occurred prior to start of treatment.

Other Action Taken for Event

- 1 = None (ie, no treatment was required)
- 2 = Medication required (ie, prescription and/or OTC medication was required to treat the AE)
- 3 = Hospitalisation or prolongation of hospitalisation required (ie, hospitalisation was required or prolonged because of the AE, whether medication was required)
- 4 = Other

Adverse Event Outcome

- 1 = Recovered/Resolved (ie, the participant fully recovered from the AE with no residual effect observed)
- 2 = Recovering/Resolving (ie, the AE improved but has not fully resolved)
- 3 = Not Recovered/Not Resolved (ie, the AE itself is still present and observable)
- 4 = Recovered/Resolved with Sequelae (ie, the residual effects of the AE are still present and observable, including sequelae/residual effects)
- 5 = Fatal (ie, 'fatal' should be used when death is a direct outcome of the AE)
- 6 = Unknown

Clinical Laboratory Changes

Any abnormality in a laboratory value that is new in onset or which has worsened in severity or frequency from the baseline condition and meets 1 of the following criteria will be recorded on the AE pages of the eCRF:

- Requires therapeutic intervention or diagnostic tests
- Leads to discontinuation of IP
- Has accompanying or inducing symptoms or signs
- Is judged by the investigator as clinically significant

Combined elevations of aminotransferases and bilirubin, either serious or nonserious, and whether causally related, meeting the criteria of a potential Hy's Law case (total bilirubin level $\geq 2 \times$ upper limit of normal [ULN] with simultaneous ALT or AST $\geq 3 \times$ ULN) should always be reported to the sponsor as soon as possible following the procedures outlined in Section 10.2 for SAE reporting, with the investigator's assessment of seriousness, causality, and a detailed narrative.

Overdose

Any instance of overdose (suspected or confirmed) must be fully documented as an AE or SAE if it meets the SAE criteria. Details of any signs or symptoms and their management should be recorded including details of any antidote(s) administered.

Adverse Event Follow-up

All AEs will be followed until resolved or stable and the outcome documented on the eCRF. If the investigator detects an AE in a study participant after the last scheduled follow-up visit and

considers the event possibly related or related to prior study treatment, the investigator will document it.

Serious Adverse Events (SAE)/Serious Adverse Drug Reaction (SADR)

Definition: A serious adverse event (SAE)/Serious Adverse Drug Reaction (SADR) is an AE occurring during any study phase (i.e., run-in, treatment, washout, follow-up), and at any procedure, that fulfills one or more of the following criteria:

- Results in death
- Is immediately life-threatening
- Requires inpatient hospitalization or prolongation of existing hospitalization
- Results in persistent or significant disability or incapability
- Is a congenital abnormality or birth defect
- Is an important medical event that may jeopardize the patient or may require medical intervention to prevent one of the outcomes listed above

Any serious, untoward event that may occur subsequent to the reporting period that the investigator assessed as related to IP should also be reported and managed as an SAE. The investigator should follow participants with AEs until the event has resolved or the condition has stabilized. In case of unresolved AEs, including significant abnormal clinical laboratory values at the end of study assessment, these events will be followed until resolution or until they become clinically not relevant. Disability/incapacitating: An AE is incapacitating or disabling if the experience results in a substantial and/or permanent disruption of the participant's ability to carry out normal life functions.

The causality of SAEs/SADRs (i.e., their relationship to study treatment) will be assessed by the investigator(s). Note that SAEs/SADRs that could be associated with any study procedure should also be reported. For such events the causal relationship is implied as "yes".

Serious unexpected adverse drug reaction (SUADR) Definition: means a serious adverse drug reaction (SADR) that is not identified in nature, severity or frequency in the risk information set out in the investigator's brochure or on the label of the drug.

Reporting of SAEs/SADRs/SUADRs

All SAEs/SADRs/SUADRs should be reported to the sponsor immediately. The immediate reports should be followed promptly by detailed, written reports. The immediate and follow-up reports should identify subjects by unique code numbers assigned to the trial subjects rather than by the subjects' names, personal identification numbers, and/or addresses.

The QI should comply with the applicable regulatory requirement(s) related to the reporting of serious unexpected adverse drug reactions to the regulatory authority(ies) and the REB.

SAEs/SADRs: The sponsor-investigator will comply with any and all national rules and regulations concerning safety reporting (SADRs or SAEs as required). All SAEs/SADRs (according to the definition in ICH GCP) will be done by the investigator in accordance with local regulations and reported to the appropriate regulatory bodies.

SUADRs: In accordance with section C.05.014 of the Regulations, it is the responsibility of a sponsor to inform Health Canada, in an expedited manner, of all **SUADRs** in respect of a drug during the course of a Phase I-III clinical trial, whether or not the event occurred inside or outside of Canada:

- a. this information must be submitted **within 15 calendar days** after becoming aware of the event if it is neither fatal nor life threatening
- b. if the event is **fatal or life threatening**, Health Canada must be advised of the event **within 7 calendar days** after the sponsor first became aware of it.

In cases where the event is **fatal or life threatening**, the sponsor must submit a **complete report** to Health Canada **within 8 calendar days** after the first notification (initial report) to Health Canada of the event. Follow-up reports of fatal or life threatening reactions must include an assessment of the importance of the event and the implication of any findings, including relevant previous experience with the same or similar drugs.

In addition, in keeping with ICH GCP, the sponsor should expedite reporting of all SUADRs to all concerned QI(s)/institution(s), the REB(s) where required (ICH E6, 5.17.1).

Statistical analysis plan

Data will be analyzed for a modified intent-to-treat set: the full analysis set (FAS) will comprise all patients who received at least one dose of study medication and had at least one valid post-baseline assessment of the primary outcome.

- The MMRM model will use study visit as a fixed factor and the interaction between treatment and visit to allow for estimation of treatment effect at specific time points. Additionally, the interaction term of visit and baseline to allow for time dependent adjustment of baseline. An unstructured covariance matrix will be used.

To control for type I error, the following sequence of hierarchically ordered primary and key secondary end points will be used at a significance level of 0.05 1-sided for the primary outcome:

- Primary endpoint: Change from baseline to week 8 between vortioxetine and placebo in DSST performance score
- Secondary endpoint: Change from baseline to week 2 between vortioxetine and placebo in DSST performance score

The change from baseline in DSST performance score after 8 weeks of treatment will be analyzed with a one-sided mixed model for repeated measures (MMRM) with treatment and study visits as fixed factors and baseline DSST performance as covariate. For secondary analyses, the change from baseline in DSST, CogState Online Cognitive Battery, PDQ-20, TMT-A/B, SHAPS, FSS, GAD-7, WHO-5, EQ-5D-5L, BAS, RPE, RAVLT, PCFS, EEfRT, SETS, QIDS-SR16, IPAQ and SDS will also be analyzed using a mixed model for repeated measures (MMRM) using all available data. Withdrawal rates will be compared between placebo- and vortioxetine-randomized participants at week 8.

A power calculation was obtained via computer simulations on the primary outcome of difference in the change from baseline in DSST performance score between vortioxetine and placebo. Assuming an SD of 8.0 for the change from baseline in the DSST performance score

at week 1 and a 15% dropout rate, based on previous randomized, placebo-controlled trials with vortioxetine, it was calculated that 100 subjects (modified per treatment group) are required to achieve 80% power to detect a difference of 3.1 in the change from baseline in DSST performance score between vortioxetine and placebo (i.e., Cohen's $d=0.38$) by an MMRM with a 1-sided significance level of $p<0.05$ ^{26,53}.

The magnitude of fMRI-determined ventral striatal (including nucleus accumbens) activation during anticipation of gain versus no-incentive trials, as well as loss versus no-incentive trials, in the EEfRT task. Mean and maximum fMRI ventral striatal activation will be assessed.

Publication Plan

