- Patients on other antidepressants are allowed to participate only if the antidepressant is prescribed at subtherapeutic doses for a primary indication other than mood disorders. Participants will be made aware in the consent form that the combination of the two antidepressants would be considered investigational and that the safety/efficacy profiles are unknown ²⁸⁻³⁰.
- Current alcohol or substance use disorder.
- Inability to provide consent.
- Current alcohol and/or substance use disorder as confirmed by the M.I.N.I 7.0.2.
- Presence of comorbid psychiatric disorder that is a primary focus of clinical concern as confirmed by the M.I.N.I. 7.0.2.
- Medications approved and/or employed off-label for cognitive dysfunction (e.g., psychostimulants).

- Any medication for a general medical disorder that, in the opinion of the investigator, may affect cognitive function.
- Use of benzodiazepines within 12 hours of cognitive assessments.
- Consumption of alcohol within 8 hours of cognitive assessments.
- Physical, cognitive, or language impairments sufficient to adversely affect data derived from cognitive assessments.
- Diagnosed reading disability or dyslexia.
- Clinically significant learning disorder by history.
- Electroconvulsive therapy (ECT) in the last 6 months.
- History of moderate or severe head trauma (e.g., loss of consciousness for >1 hour), other neurological disorders, or unstable systemic medical diseases that in the opinion of the investigator are likely to affect the central nervous system.
- Pregnant and/or breastfeeding.
- Received investigational agents as part of a separate study within 30 days of the screening visit.
- Actively suicidal/presence of suicidal ideation or evaluated as being at suicide risk (as per clinical judgment).
- Currently receiving treatment with Monoamine Oxidase Inhibitors (MAOIs) antidepressants, antibiotics such as linezolid, or intravenous methylene blue.
- Previous hypersensitivity reaction to vortioxetine or any components of the formulation. Angioedema has been reported in patients treated with vortioxetine.
- Serotonin syndrome.
- Abnormal bleeding.
- Previous history of mania/hypomania.
- Angle closure glaucoma.
- Hyponatremia.
- Moderate hepatic impairment.
- Active seizure disorder/epilepsy, not controlled by medication (per study physician assessment).
- Presence of any unstable medical conditions.

Recruitment

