Perceived Deficits Questionnaire-20 (PDQ-20), Generalized Anxiety Disorder-7 (GAD-7), Snaith-Hamilton Pleasure Scale (SHAPS), Fatigue Severity Scale (FSS), Post-Covid Functional Scale (PCFS), World Health Organization-5 (WHO-5), Sheehan Disability Scale (SDS), Behavioural Activation Scale (BAS), 5-Level EQ-5D version (EQ-5D-5L), Quick Inventory of Depressive Symptoms (16-Item) (Self-Report) (QIDS-SR16) and International Physical Activity Questionnaire (IPAQ) assessed at weeks 0, 2, 4 and 8.

Conditions for Withdrawal From the Study

Premature Discontinuation

If participation in the study is terminated prematurely for any reason, the reason for such early termination should be documented. The reason for any early termination should be recorded, providing as much information as possible.

The reason for early termination can be selected from as follows:

- Screen Failure: Participant does not qualify to participate in the study.
- Lack of efficacy (e.g., increased suicidality).
- Adverse Event: Clinical or laboratory events occurred that, in the medical judgment of the investigator for the best interest of the participant, are grounds for discontinuation. This includes serious and non-serious AEs regardless of relation to study medication.
- Death: The participant died.
- Withdrawal of Consent: The participant desired to withdraw from further participation in the study in the absence of an investigator-determined medical need to withdraw. If the participant gave a reason for withdrawing, it should be recorded in the eCRF.
- Protocol Violation: The participant's findings or conduct failed to meet the protocol entry criteria or failed to adhere to the protocol requirements (e.g., drug non-compliance, failure to return for a defined number of visits, becoming pregnant during trial). The violation necessitated early discontinuation from the study.
- Lost to Follow-Up: The participant stopped coming for visits and study personnel were unable to contact the participant.

- Non-compliance: The participant was non-compliant with study visits or procedures.
- Other: The participant was discontinued for a reason other than those listed above.

Withdrawal Procedures and Next Steps

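### Increased suicidality is the only example given of a lack-of-efficacy withdrawal, so such a case could be missing from adverse-event withdrawals in a table by reason

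*Combined protocol and SAP*

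**What the plan says.** Under Conditions for Withdrawal From the Study, Premature Discontinuation, the protocol requires a reason for every early termination and introduces the list with "The reason for early termination can be selected from as follows". One reason is "Lack of efficacy (e.g., increased suicidality". The next is Adverse Event, for clinical or laboratory events that the investigator judges to be grounds for discontinuation. On its scope the protocol adds: "This includes serious and non-serious AEs regardless of relation to study medication".

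Four other places bear on the point:

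- **Side effects** (under Study Medication: Vortioxetine) includes "Clinical worsening or suicide risk" in the rare band, below 1%.
- **Exclusion Criteria** rules out anyone who is "Actively suicidal/presence of suicidal ideation or evaluated as being at suicide risk (as per clinical judgment".
- **Adverse Events** defines an event as "the development of an undesirable medical condition or the deterioration of a pre-existing medical condition" during or after exposure, whether or not the product is thought to be the cause.
- **Recordings of Adverse Events** asks for every event to be recorded. The fields include the action taken on the product, seriousness, and the outcome where the event led the patient to stop the product.

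The Statistical analysis plan has one sentence on withdrawal: "Withdrawal rates will be compared between placebo- and vortioxetine-randomized participants at week 8".

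**The concern.** The hypothesis and the primary outcome concern cognition, and no listed outcome is a dedicated measure of suicidality. New suicidality in a participant who had none at entry would ordinarily be read as a possible harm. The one worked example in the withdrawal list instead sends staff to a reason that is not a safety reason.

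Two things are at stake. If withdrawals are tabulated by reason, a suicidality case coded as the example suggests would be counted under lack of efficacy and not under adverse events. For the same participant, the adverse-event record could also show an event that led to stopping the product while the withdrawal form shows lack of efficacy. The protocol does not say which record governs.

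**Working it through.** The plan states no figure on this point, so the check is mainly a comparison of texts. A short calculation of scale follows.

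**Does on-study suicidality meet the protocol's own definition of an adverse event?**

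1. The definition covers a new undesirable condition or the worsening of an existing one, with no requirement of causality.
2. Suicidal ideation, or judged suicide risk, excludes a person at entry. Suicidality that appears on study would therefore normally be new or worsened.
3. The side-effect list names suicide risk, so the protocol itself treats it as a possible effect of the drug.
4. It therefore meets the definition. If the investigator judges it grounds for discontinuation, it also meets the Adverse Event withdrawal reason, which contains no exception for suicidality.

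**Which withdrawal reason applies?** Two fit: Adverse Event by its scope, and lack of efficacy by its example. The list gives no order of priority. The documents do not say whether more than one reason may be recorded. The coding is therefore ambiguous, and the only explicit example points away from safety.

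**What would a miscoded case change?**

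| Output | Affected? | Why |
|---|---|---|
| Overall withdrawal rate by arm at week 8 | No | The participant counts as withdrawn under either reason |
| Adverse-event listing | No | Every event is recorded independently of the withdrawal reason |
| Stopping of product due to an adverse event, counted from adverse-event records | Not necessarily | The record has its own field for this |
| Withdrawals by reason, if tabulated | Yes | The case moves from adverse event to lack of efficacy |
| Agreement between withdrawal form and adverse-event record | Could fail | No rule links the two |

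**How many cases?** Inputs are 100 participants on vortioxetine (Sample Size), a frequency below 1% for the rare item (Side effects), and 15% dropout (Statistical analysis plan). The documents give only the upper limit of 1%, so I take true rates p of 0.1%, 0.5% and 1% as assumptions. I also assume that every case leads to withdrawal.

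- Expected cases = 100 × p
- P(at least one) = 1 − (1 − p)^100
- P(at least two) = 1 − (1 − p)^100 − 100p(1 − p)^99

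| p | Expected | At least one | At least two |
|---|---|---|---|
| 0.1% | 0.1 | 9.5% | 0.5% |
| 0.5% | 0.5 | 39.4% | 9.0% |
| 1% | 1.0 | 63.4% | 26.4% |

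At the 1% ceiling the chance of three or more is 7.9%, so 0 to 2 is a fair plausible range. Even at that ceiling, the chance of no case at all is 100% − 63.4% = 36.6%.

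For comparison, 15% of 100 is 15 withdrawals per arm, and one case is 1/15 = 6.7% of them. That is a share of all withdrawals. The share of adverse-event withdrawals cannot be worked out, because the documents do not say how many of the 15 are expected for that reason.

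**The case against.** The strongest reply is that no planned analysis is affected. The only stated withdrawal comparison is of overall rates, which recoding cannot alter. Safety outcomes are spontaneously reported adverse events and laboratory tests; withdrawal due to adverse events is not a named outcome. Events are recorded separately with their effect on continued dosing, and a serious case must be reported to the sponsor at once. All of this stands, and it limits the point to withdrawals by reason and to agreement between records.

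It can also be said that worsening suicidality is not wholly foreign to efficacy here. QIDS-SR16 is a secondary outcome and is described as covering the symptom domains of a major depressive episode. The section on transition to standard care judges benefit by mood as well as cognition, and the side-effect item itself joins clinical worsening to suicide risk. This has some weight, so it would be too absolute to say that the trial's efficacy measures have nothing to do with mood. It does not remove the conflict: the event still meets the adverse-event definition, and the Adverse Event reason applies whatever the cause.

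A reader might go further and infer that safety withdrawals will be under-counted, that a signal could vanish, or that missing-data handling would be misled. The documents do not support these readings. The Adverse Event reason remains available for the same case, and the event stays in the adverse-event data. The planned mixed model for repeated measures and the full analysis set make no use of the reason for withdrawal.

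Nor should the band below 1% be applied to both arms or to suicidality alone. It is given for vortioxetine, for a combined item, and no placebo figure is stated.

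**Conclusion.** The inconsistency is real and should be corrected, but its reach is modest. The example given for lack of efficacy conflicts with the protocol's own side-effect list, entry criteria and adverse-event definition. As a result, withdrawals due to adverse events could be under-counted in a table by reason, and two records for one participant could disagree.

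Fewer than one case is expected among 100 vortioxetine participants, and about 0 to 2 is plausible. This assumes that the stated band carries over to this population and to eight weeks of treatment, and that each case leads to withdrawal. Because the band covers clinical worsening as well, suicidality alone may be rarer. The case for acting rests on the seriousness of a single event and the very low cost of the correction, not on any effect on the trial's statistical results.

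**What to change.** Reconcile the withdrawal-reason list with the side-effect list, the adverse-event definition and the adverse-event recording section:

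1. Remove the suicidality example from lack of efficacy, and state that withdrawals for increased suicidality are classified under the Adverse Event reason.
2. State that withdrawals due to adverse events are counted consistently with the discontinuation field of the adverse-event record.

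The cost is one line in the list and its eCRF counterpart, plus one sentence on counting. If any participants have already been withdrawn for lack of efficacy, their forms should be checked against their adverse-event records. The change is one of classification only; when treatment should be stopped is left as it is.

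No change to sample size, the primary analysis or the planned comparison of withdrawal rates is needed.
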